10.5. Biopsy and Surgical Pathology

Immediately following biopsy or surgery, the specimens will be sent for histopathological processing and analysis at the site in accordance with the study Pathology Manual.

Gross handling of the prostate gland and lymphadenectomy specimens, if applicable, will include whole gland assessment and sectioning of the entire prostate gland, overall measurement of specimen size, lesion location, dissection and description (including location) of identified lymph nodes, and submission of lymph nodes in their entirety plus all remaining fibroadipose tissue for each harvested regional packet. Histopathology results of the prostate gland and pelvic lymph nodes (Cohort A) or biopsy location (Cohort B) will be recorded in the eCRF.

Should a Cohort A subject forego RP surgery and undergo alternative procedure for prostate cancer (e.g., biopsy), the procedure and corresponding histopathology data will be recorded in the eCRF. Likewise, should a Cohort B subject receive additional procedure for prostate cancer, the procedure and corresponding histopathology data will be recorded in the eCRF.

10.6. Pharmacokinetics

A total of 10 subjects from either cohort at the JHU site will complete the pharmacokinetics (PK) portion of the study. For detailed instructions on sample collection, processing, and analysis, please refer to the PK Manual.

A 4.5 mL blood sample will be collected at the following nine time points: pre-dose, 5 ± 2 m, 15 ± 2 m, 30 ± 5 m, 1 ± 0.25 hr, 2 ± 0.25 hr, 4 ± 0.25 hr, 6 ± 0.25 hr, and 8 ± 0.25 hr post-dose.

Urine samples will be collected over the following intervals: 0-2 hr, 2-4 hr and 4-8 hr post dose.

Whole body PET/CT scans will be collected at three time points: up to 17 minutes after PyL injection and prior to voiding, 1 ± 0.25 hr and 4 ± 0.25 hr post dose.

Procedure	Pre- dose	0 hr	5±2 m	15± 2 m	30± 5 m	1± 0.25 hr	2± 0.25 hr	3± 0.25 hr	4± 0.25 hr	6± 0.25 hr	8± 0.25 hr
¹⁸ F-DCFPyL Administration		Х									
Blood & Plasma Collection	X		Х	Х	Х	X	X		Х	Х	Х
Urine Collection		<	<x> <x></x></x>				>				
¹⁸ F-DCFPyL PET/CT Imaging			X			X			Х		

 Table 5:
 PK Sampling & Imaging Timepoints

Analysis will be generated as described below and in Section 12.5.4. Aliquots of blood, plasma and urine samples will be batch counted in an automated gamma counter immediately following the sample collection period. Resulting raw radioactivity counts will be converted into radioactivity concentrations using an aliquot of the dosing formulation as a reference standard.

Blood concentration-time data will be computed by non-compartmental analysis and pharmacokinetic parameters, e.g., C_{max} , AUC, CL, V_{ss} , and MRT will be generated. Ratios of blood to plasma radioactivity at each time point will be calculated.

The total amount of excreted radioactivity per urine collection interval will be calculated as a product of urine radioactivity concentration and volume, and then expressed as a percent of administered dose.

Metabolic profiles in urine will be determined using radio-chromatographic methods. The areas under the radio-chromatographic peaks corresponding to the parent compounds and putative metabolites, if applicable, will be used in the qualitative assessment of metabolic profiles in urine.

Whole-body PET/CT images acquired immediately after PyL injection and at 1 hr and 4 hr postdose will be used to obtain volumes and activity concentrations for selected tissues/organs. Based on these data, time-integrated activity coefficients will be derived and may be used for subsequent calculation of radiation absorbed doses using the OLINDA/EXM software. This analysis will be described in a dosimetry report for ¹⁸F-DCFPyL.

11. ASSESSMENT OF SAFETY

11.1. Safety Parameters

11.1.1. Demographic/Medical History

Demographic and baseline information, including date of birth, race, and ethnicity, will be collected.

A complete prostate medical history will be obtained at the first screening visit. Prostate medical history includes review of prostate disease history, prostate cancer staging, PSA results, biopsy results, and all past/present therapies.

Other clinically relevant medical history will be collected prior to study drug administration. This should include any past and/or current medical conditions that, in the opinion of the investigator, are clinically relevant regardless of whether it has resolved. Special attention should be paid to prior malignancies other than prostate cancer or concurrent or past conditions that can change pelvic anatomy or cause lymphadenopathies (e.g., viral, bacterial or parasitic infections).

11.1.2. Vital Signs

Vital sign measurements will include temperature, respiratory rate, blood pressure, and heart rate. All measurements should be obtained from the subject in the sitting position and measured at two intervals on the day of dosing, including pre-dosing and pre-imaging.

11.1.3. Weight and Height

Height, weight, and BMI at screening will be captured.

11.1.4. Electrocardiogram (ECG)

A 12-lead electrocardiogram (ECG) will be taken at two intervals on the day of dosing, including prior to dosing and prior to imaging. Please refer to the ECG Procedure Manual for acquisition and transmittal details. The onsite Investigator has the responsibility to evaluate the ECG for the assessment of subject safety. Adverse events will be reported in the CRF.

11.1.5. Laboratory Assessments

11.1.5.1. Hematology, Blood Chemistry, PSA and Testosterone

A blood draw will be collected at the screening and follow-up visits as stated in Table 6. Clinical hematology and blood chemistry will be evaluated for safety monitoring. If PSA and testosterone have not been tested within 30 days of study drug injection, a blood draw will be collected prior to dosing.

Category	Analytes	Frequency 1
Hematology	CBC: WBC differential (neutrophils, lymphocytes, monocytes, eosinophils, basophils), WBC count, RBC count, Hematocrit, Hemoglobin, Platelets	Screening, Follow-Up
Chemistry	CMP: Sodium, Potassium, Calcium, Chloride, Glucose, BUN, Creatinine, Total Bilirubin, ALT, AST, Alkaline Phosphatase, Albumin, Total Protein	Screening, Follow-Up
PSA	Total	Screening
Testosterone	Total	Screening

Table 6: Clinical Laboratory Tests

CBC=complete blood count; WBC=white blood cell; RBC=red blood cell; CMP=comprehensive metabolic panel; BUN=blood urea nitrogen; ALT=alanine aminotransferase; AST=aspartate aminotransferase; PSA=prostate-specific antigen

¹ Blood draws and laboratory testing will be conducted according to local standard practices. PSA and testosterone resulted within 30 days of Day 1 does not need to be re-tested.

11.2. Adverse and Serious Adverse Events

11.2.1. Definition of Adverse Events

11.2.1.1. Adverse Event (AE)

An AE is the development of an undesirable medical occurrence or the deterioration of a preexisting condition following or during exposure to a pharmaceutical product, whether or not considered related to the product.

All AEs (related and unrelated) will be collected on the day of, after ¹⁸F-DCFPyL dosing and at time of follow-up visit (pre-surgery/biopsy). Adverse events will also be assessed via a safety phone call at the following timepoints, if applicable: 1) 7 (\pm 3) days post study drug injection (if surgery or biopsy has not yet occurred), and 2) 21 (\pm 7) days post biopsy.

All AEs, whether or not they are related to study drug, must be recorded on the study case report forms.

11.2.1.2. Serious Adverse Event (SAE)

A serious adverse event is an AE that fulfils one or more of the following:

- Results in death
- It is immediately life-threatening
- It requires in-patient hospitalization or prolongation of existing hospitalization
- It results in persistent or significant disability or incapacity

- Results in a congenital abnormality or birth defect of a subject's child
- It is an important medical event that may jeopardize the patient or may require medical intervention to prevent one of the outcomes listed above.

All SAEs that occur after any patient/subject has been dosed until study completion, whether or not related to the study, must be recorded on forms provided by the Sponsor, or designee.

11.3. Relationship to Study Drug

The Principal Investigator or Sub-Investigator must make the determination of relationship to the investigational product for each AE (Unrelated or Related). The Investigator should decide whether, in his or her medical judgment, there is a reasonable possibility that the event may have been caused by the investigational product. If no valid reason exists for suggesting a relationship, then the AE should be classified as "unrelated." If there is any valid reason, even if undetermined, for suspecting a possible cause-and-effect relationship between the investigational product and the occurrence of the AE, then the AE should be considered "related."

11.4. Recording Adverse Events

Adverse events spontaneously reported by the patient/subject and/or in response to an open question from the study personnel or revealed by observation will be recorded during the study at the investigational site.

The investigator should assess all clinical laboratory results for clinical significance and record the assessment in source documents. The investigator should evaluate any laboratory result change from pre- and post-study drug administration to determine if the change meets the definition of an AE or SAE. Record any clinically significant lab results determined to meet the definition of an AE and SAE on the AE eCRF and SAE Report Form, respectively.

Information about AEs and SAEs will be collected from the first administration of study drug until the pre-surgery/biopsy follow-up visit. The AE term should be reported in standard medical terminology and be the medical diagnosis when possible. For each AE, the investigator will evaluate and report the onset (date and time), resolution (date and time), intensity, causality, action taken, serious outcome (if applicable), and whether or not it caused the patient to discontinue the study.

Intensity will be assessed according to the NCI CTCAE, version 4.03. If the CTCAE grading is not defined in the NCI CTCAE grading table for a particular AE, severity will be rated according to the following definitions

- Mild (awareness of sign or symptom, but easily tolerated)
- Moderate (discomfort sufficient to cause interference with normal activities)
- Severe (incapacitating, with inability to perform normal activities)
- Life Threatening (immediate risk of death from the event as it occurred)
- Death (death related to adverse event)

It is important to distinguish between serious and severe AEs. Severity is a measure of intensity whereas seriousness is defined by the criteria under Section 11.2.1.2. An AE of severe intensity may not be considered serious.

Should a pregnancy occur, it must be reported and recorded on the Sponsor's pregnancy form. Pregnancy in itself is not regarded as an AE.

The outcome of all pregnancies (spontaneous miscarriage, elective termination, normal birth or congenital abnormality) must be followed up and documented even if the patient was discontinued from the study.

All reports of congenital abnormalities/birth defects are SAEs. Spontaneous miscarriages should also be reported and handled as SAEs. Elective abortions without complications should not be handled as AEs.

11.5. Reporting Serious Adverse Events

All SAEs (related and unrelated) will be recorded at the same interval defined for AE collection as indicated in Section 11.2.1.1. Any SAEs considered possibly or probably related to the investigational product and discovered by the Investigator at any time after the study should be reported. All SAEs must be reported to Progenics or designee within 24 hours of the first awareness of the event. The Investigator must complete, sign and date the SAE pages, verify the accuracy of the information recorded on the SAE pages with the corresponding source documents, and send a copy by email or fax to Sponsor, or designee.

Additional follow-up information, if required or available, should promptly be emailed or faxed to Sponsor, or designee via a follow-up SAE form and placed with the original SAE information and kept with the appropriate section of the CRF and/or study file.

Progenics Pharmaceuticals, Inc. is responsible for notifying the relevant regulatory authorities of certain events. It is the Principal Investigator's responsibility to notify the IRB or IEC of all SAEs that occur at his or her site. Investigators will also be notified of all unexpected, serious, drug-related events (7/15 Day Safety Reports) that occur during the clinical trial. Each site is responsible for notifying its IRB or IEC of these additional SAEs.

12. STATISTICS

12.1. Sample Size

Approximately 262 subjects will be dosed in cohort A. No formal power calculations will be performed for cohort B; reliable estimates should be achievable from approximately 115 dosed. This results in a total sample size of approximately 377 subjects dosed in the study.

The primary analysis in Cohort A will test the co-primary endpoints of sensitivity and specificity of ¹⁸F-DCFPyL PET imaging relative to histopathology for metastatic disease in preprostatectomy patients. For each co-primary endpoint there will be three independent imaging readers. At least two of the three readers must reject the null hypothesis for specificity to be deemed a success. If specificity is a success, then the same two readers need to reject the null

hypothesis for sensitivity to reach overall success of the primary endpoint. The null hypotheses will be tested in the following order:

- 1. Specificity of ¹⁸F-DCFPyL PET/CT imaging relative to histopathology in cohort A H₀: $\pi_{Sp} = 0.80$ versus H₁: $\pi_{Sp} \neq 0.80$,
- 2. Sensitivity of ¹⁸F-DCFPyL PET/CT imaging relative to histopathology in cohort A

H₀: $\pi_{Se} = 0.40$ versus H₁: $\pi_{Se} \neq 0.40$

where π_{Se} is the true sensitivity and π_{Sp} is the true specificity of ¹⁸F-DCFPyL PET imaging.

A total of approximately 262 subjects from Cohort A will provide 80% power to reject the null hypothesis about sensitivity at the 5% significance level if the true sensitivity is at least 60% and at least 80% power to reject the null hypothesis about specificity at the 5% significance level if the true specificity is at least 87.8%. These calculations are based on the following assumptions:

• the probability of a positive histopathology sample in Cohort A is 20%,

The sample size is based on the normal approximation to the binomial distribution without a continuity correction⁴⁸:

$$n \ge \left\{ \frac{z_{\alpha/2} \sqrt{P_0(1-P_0)} + z_\beta \sqrt{P_1(1-P_1)}}{P_1 - P_0} \right\}^2$$

 P_0 are P_1 are values of sensitivity under the null and alternative hypotheses, respectively. After adjusting sensitivity and specificity separately by their corresponding prevalence values, a total in 236 evaluable subjects are needed in cohort A. Assuming 10% drop out or non-evaluable rate increases the required number of subjects in cohort A to approximately 262.

The type I error rate of 5% will be preserved by requiring that both null hypotheses be rejected in order to draw the conclusion that ¹⁸F-DCFPyL is efficacious for imaging. The second primary endpoint is only tested if the first primary endpoint is rejected at 5% per a fixed sequential method. If the first hypothesis fails to be rejected, no further testing will be conducted.

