12.5.2. Efficacy Analysis

12.5.2.1. Primary Endpoint

Cohort A

The primary analysis in Cohort A will be addressed by computing point estimates and 95% twosided confidence intervals (CIs) for specificity first and if the null hypothesis is rejected for specificity then sensitivity will be tested next. Both outcomes are on the subject level (one overall outcome per subject) in the evaluable set. If the *per protocol* population exists then this analysis will be performed on the *per protocol* population as a supplemental analysis. The normal approximation to the binomial distribution will be used. Sensitivity and specificity will be computed for each of three central imaging core lab independent readers.

The null hypothesis for specificity will be rejected if the lower limit of the 95% CI exceeds 0.80 for at least two readers. If statistical significance is achieved for specificity where the null hypothesis is rejected, then sensitivity will be tested where the null hypothesis will be rejected if the lower limit of 95% CI exceeds 0.40 for the same two readers who rejected the null hypothesis for specificity.

A sensitivity analysis will be performed to allow any 2 of the 3 central readers to reject the null hypothesis for sensitivity only after specificity has been deemed a success. This analysis will not require the same 2 central readers to reject the null hypothesis for specificity and sensitivity. This analysis will be performed for the evaluable and per protocol populations.

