## 4.3. Sample Size

The primary analysis in Cohort A will test the co-primary endpoints of sensitivity and specificity of F-DCFPyL PET imaging relative to histopathology for the evaluable set of subjects in Cohort A with metastatic disease. For each co-primary endpoint, there will be three independent imaging readers. At least two of the three readers must reject the null hypothesis for specificity to be deemed a success. If specificity is a success, then the same two readers need to reject the null hypothesis for sensitivity leading to overall success of the primary endpoint. The null hypotheses will be tested in the following order:

- 1. Specificity of F-DCFPyL PET imaging relative to histopathology in Cohort A  $H_0$ :  $\pi_{Sp} = 0.80$  versus  $H_1$ :  $\pi_{Sp} \neq 0.80$
- 2. Sensitivity of F-DCFPyL PET/CT imaging relative to histopathology in Cohort A  $H_{01}$ :  $\pi_{Se} = 0.40$  versus  $H_{11}$ :  $\pi_{Se} \neq 0.40$

where  $\pi_{Se}$  is the true sensitivity and  $\pi_{Sp}$  is the true specificity of F-DCFPyL PET imaging.

A total of 262 subjects from Cohort A will provide 80% power to reject the null hypothesis about sensitivity at the 5% significance level if the true sensitivity is at least 60% and at least 80% power to reject the null hypothesis about specificity at the 5% significance level if the true specificity is at least 87.8%. These calculations are based on the following assumptions:

• the probability of a positive histopathology sample in Cohort A is 20%,

The sample size is based on the normal approximation to the binomial distribution without a continuity correction.

$$n \ge \left\{ \frac{z_{\alpha/2} \sqrt{P_0(1 - P_0)} + z_{\beta} \sqrt{P_1(1 - P_1)}}{P_1 - P_0} \right\}^2$$

where P0 are P1 are values of sensitivity under the null and alternative hypotheses, respectively. After adjusting sensitivity and specificity separately by their corresponding prevalence values, a total in 236 subjects are needed. Assuming a 10% drop out or non-evaluable rate increases the required number of subjects in Cohort A to 262.

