## 7.5. Multiple Comparisons and Multiplicity

Within Cohort A, the type I error rate will be preserved by requiring that both null hypotheses be rejected in order to draw the conclusion that F-DCFPyL is efficacious for imaging. In addition, the three readers from the central imaging core laboratory are independent and requiring that the same 2 of 3 readers agree about sensitivity and specificity (Cohort A) will control for type I error.

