## 7.6. Analysis of the Primary Efficacy Endpoint

### 7.6.1. Primary Efficacy Analysis of Primary Endpoints

The primary analysis for subjects in Cohort A will be addressed by computing point estimates and 95% two-sided confidence intervals (CIs) for specificity first and if the null hypothesis is rejected for specificity then sensitivity will be tested next. Both outcomes are assessed on the subject level (one overall outcome per subject) in the *evaluable set*. If the *per protocol* set exists, then this analysis will be performed on the *per protocol* set as a supplemental analysis. The normal approximation to the binomial distribution is planned assuming the assumptions have been met (See Section 7.2). Sensitivity and specificity will be computed for each of three central imaging core lab independent PET/CT readers.

The null hypothesis for specificity will be rejected if the lower limit of the 95% CI exceeds 80% for at least two of the three independent central PET/CT readers. If statistical significance is achieved for specificity where the null hypothesis is rejected, then sensitivity will be tested where the null hypothesis will be rejected if the lower limit of the 95% CI exceeds 40% for the same two readers who rejected the null hypothesis for specificity.

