#### 7.9.2. Inter-Reader Reliability

For the primary analysis of the primary endpoint the inter-reader reliability will be estimated using the multiple-reader generalized kappa statistic developed by Fleiss.

$$Kappa = \frac{\bar{p} - \bar{p}_e}{1 - \bar{p}_e}$$

Variance: 
$$\frac{2}{NK(K-1)} \frac{\sum_{j=1}^{R} p_j^2 + (\sum_{j=1}^{R} p_j^2)^2 - 2\sum_{j=1}^{R} p_j^3}{(1 - \sum_{j=1}^{R} p_j^2)^2}$$

Where

$$p_j = \frac{1}{NK} \sum_{i=1}^{N} n_{ij}$$

$$p_i = \frac{\sum_{j=1}^{R} n_{ij} (n_{ij} - 1)/2}{K(K-1)/2}$$

$$\bar{p} = \frac{\sum_{i=1}^{N} p_i}{N}$$
 (overall agreement)

$$\bar{p}_e = \sum_{j=1}^R p_j^2$$
 (expected chance agreement)

The generalized Kappa statistic and a 95% confidence interval will be computed.

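### The stated 80% power for sensitivity is per reader and per hypothesis; under the plan's own success rule, power at the design values is about 68% to 76%

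*Protocol*

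**What the plan says.** Protocol 12.1 states that "A total of approximately 262 subjects from Cohort A will provide 80% power to reject the null hypothesis about sensitivity" at the 5% level if true sensitivity is at least 60%, and gives at least 80% power for specificity if it is at least 87.8%. Both rest on a formula for a single proportion (normal approximation, no continuity correction). The total of 236 evaluable subjects is reached "After adjusting sensitivity and specificity separately by their corresponding prevalence values", and a 10% loss raises it to about 262. SAP 4.3 repeats this.

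The same sections set the success rule. At least two of three central readers must reject the specificity null, and then "the same two readers need to reject the null hypothesis for sensitivity leading to overall success of the primary endpoint". Protocol 12.1 makes the order explicit: "The second primary endpoint is only tested if the first primary endpoint is rejected at 5% per a fixed sequential method". Protocol 12.5.2.1 rejects the sensitivity null only if "the lower limit of 95% CI exceeds 0.40 for the same two readers who rejected the null hypothesis for specificity", and SAP 7.6.1 also requires this "for the same two readers who rejected the null hypothesis for specificity".

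On how the readers relate to each other, SAP 7.5 says that "the three readers from the central imaging core laboratory are independent". SAP 7.9.2 says that "the inter-reader reliability will be estimated using the multiple-reader generalized kappa statistic" but assumes no value for planning.

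**The concern.** The power statement and the success rule stand in one section but describe different events. The formula gives the chance that one reader's result on one endpoint clears its threshold. The plan's event is that at least two readers each clear both thresholds. Sensitivity cannot be declared positive unless specificity has succeeded first, so a power figure for rejecting the sensitivity null that ignores this is not the power the design has.

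What is at stake is the planning risk. A sponsor, ethics board or regulator reading Protocol 12.1 would put the chance of a failed primary at the design values at about 20%. They cannot work out the real figure from the documents, because no reader correlation is given.

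**Working it through.** **Inputs from the documents.** Two-sided 5% level (SAP 7.1). Sensitivity (Se) null 0.40, alternative 0.60; specificity (Sp) null 0.80, alternative 0.878; prevalence 20%; 236 evaluable; 10% loss (Protocol 12.1). The test is whether the lower limit of a normal-approximation 95% CI exceeds the null value (Protocol 12.5.2.1).

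**Assumptions added here.** The interval is the Wald interval. All three readers share the same true Se and Sp. Success means at least two readers who each reject both nulls. Reader correlation runs from 0 to 1, because the documents give none.

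**Step 1: the plan's own figure.** n = [(1.96·√(P0(1−P0)) + 0.8416·√(P1(1−P1))) / (P1−P0)]²

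- Sensitivity: [(0.960 + 0.412)/0.20]² = 47.09 positives; 47.09/0.20 = 235.5, so 236.
- Specificity: [(0.784 + 0.275)/0.078]² = 184.5 negatives; 184.5/0.80 = 230.6, so 231.
- The larger is 236, and 236/0.90 = 262.2, so about 262.

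The sample-size arithmetic reproduces. Nothing in it refers to readers or to the two endpoints jointly.

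**Step 2: one reader.** Let the number of positives k follow Binomial(236, 0.20). For each k, compute the exact binomial probabilities a(k) that the Se lower limit exceeds 0.40 and b(k) that the Sp lower limit exceeds 0.80. Averaged over k, these are 0.784 for sensitivity and 0.873 for specificity.

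**Step 3: the success rule.** For given k, one reader rejects both nulls with probability j(k) = a(k)·b(k).

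- Identical readers: the mean of j is 0.684.
- Independent readers: the mean of 3j²(1−j) + j³ is 0.761.

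Intermediate values were simulated with an exchangeable latent-Gaussian reader model (20,000 trials each):

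| Assumed latent reader correlation | Power of success rule |
|---|---|
| 0 (exact) | 0.76 |
| 0.3 | 0.75 |
| 0.5 | 0.74 |
| 0.8 | 0.71 |
| 0.95 | 0.69 |
| 1 (exact) | 0.68 |

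**Step 4: where the loss comes from.** Requiring two of three readers does not by itself reduce power. For sensitivity alone it gives 0.78 (identical) to 0.87 (independent), against 0.78 for one reader. The loss comes from needing both endpoints, and from needing them in the same readers. With independent readers, letting any two readers carry each endpoint (the planned sensitivity analysis) gives 0.83, so the same-reader condition costs about 7 points there.

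**Step 5: how far the range moves.**

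| Setting | Identical readers | Independent readers |
|---|---|---|
| Wald CI, random positives (main) | 0.68 | 0.76 |
| Score test matching the sample-size formula, random positives | 0.65 | 0.71 |
| Wald CI, fixed 46 / 190 | 0.65 | 0.72 |
| Wald CI, fixed 47 / 189 | 0.70 | 0.78 |
| Wald CI, fixed 48 / 188 | 0.74 | 0.84 |
| Wald CI, fixed 49 / 187 | 0.68 | 0.76 |
| Sp 0.90, Se 0.60 | 0.77 | 0.86 |
| Se 0.65, Sp 0.878 | 0.81 | 0.91 |

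The fixed-split rows jump because the smallest passing count of true positives is a whole number: 26 for 46, 47 or 48 positives, and 27 for 49. The last two rows use the main setting with a better true accuracy.

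**The case against.** The strongest reply is that the documents claim no overall power. They give one figure per hypothesis, print the one-proportion formula, say the endpoints were handled separately, and state the success rule alongside. A statistician who sees two 80% figures next to a both-must-succeed rule will know that the joint figure is lower. On this view the plan omits an operating characteristic and makes no calculation error. That is right about the arithmetic, which reproduces. It does not rescue the sensitivity statement. That figure is offered as power to reject a null which the plan lets no one reject until specificity has succeeded, and nothing marks it as applying to one reader.

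The second reply is that 68% to 76% is not the only defensible range. It depends on the interval method, a random number of positives and equal reader accuracy, and a fixed 48/188 split with independent readers exceeds 80%. This stands as a caution: the figure needs the word about and its assumptions beside it. Averaged over the planned prevalence, or at the expected 47/189 split, the rule stays below 80% across the whole range of reader correlation.

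Third, the alternatives are worded as minimum values, and a modestly better tracer restores the power. That is true, but the 80% is claimed at 60% and 87.8%. Finally, if SAP 7.5 means statistical independence, the result is the upper end, about 76%. Readers viewing the same scans would be expected to agree more than that, which moves power towards 68%.

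**Conclusion.** The concern holds. The 80% in Protocol 12.1 and SAP 4.3 is marginal power for one reader and one hypothesis. At sensitivity 0.60 and specificity 0.878, the plan's own success rule has power of about 68% (readers identical) to 76% (readers independent), a failure risk of about 24% to 32%. This rests on 236 evaluable subjects, a random number of positives at 20% prevalence, Wald intervals and three readers of equal accuracy. The score test that matches the sample-size formula lowers the range to 65% to 71%; fixing the split at 47/189 raises it to 70% to 78%. The defect is a misstated planning risk. Type I error, the decision rule and the validity of the eventual result are untouched.

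**What to change.** In Protocol 12.1 and SAP 4.3, label the two 80% figures as power per reader and per hypothesis. Then add the power of the success rule, with the assumed reader correlation (or the range over it), the interval method, the treatment of the number of positives, and the equal-accuracy assumption. Possible wording:

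> Under the success rule (specificity, then sensitivity, rejected by the same two of three readers), power at sensitivity 0.60 and specificity 0.878 with 236 evaluable subjects is about 68% if readers agree perfectly and about 76% if they are independent. This assumes normal-approximation confidence intervals, a random number of positives at 20% prevalence, and equal true accuracy for all readers.

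If the sponsor prefers a single figure, it should name the correlation behind it. If other scenarios are shown, vary each parameter in turn: specificity 0.90 with sensitivity 0.60 (about 77% to 86%), and sensitivity 0.65 with specificity 0.878 (about 81% to 91%).

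The cost is two sentences in each document and one short calculation. The stated figure becomes less favourable. Enrolment, hypotheses, decision rule and analysis do not change.
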